7.3.4 Compliance of patients

7.3.4.1 Disposition of patients

The number of patients per site are presented by treatment group and population for analysis (screened, safety set, FAS, PPS).

The disposition of patients according to their presence at the corresponding visit (performed, not-performed, drop-out) will be presented by means of frequency tables by treatment group.

The documented main reason for drop-out (adverse event, inclusion criteria not met, exclusion criteria met, non-compliance, on patient's request, contact to patient lost or other) will be presented by means of frequency tables by treatment group.

7.3.4.2 Protocol deviations

The protocol deviations will be summarized by means of frequency tables by treatment group with respect to the category (eligibility deviation, withdrawal deviation, dosing deviation, prohibited medication deviation, operational deviation) and the assessment (minor/major).

7.3.4.3 Compliance with IMP

The dispensation and return of IMPs is documented by the investigator in the Study Medication Logbook, which is part of each patients' CRF. The daily intake of the IMPs (in the morning and at noon) is documented by the patients in their diaries.

In total it is expected that each patient takes 56 of the dispensed tablets (14 days, 2 tablets in the morning and 2 tablets at noon each day).

Compliance (in %) will therefore be calculated as the number of tablets which were taken, as documented in the diary, divided by 56.

Further the ratio of returned (not used) tablets to dispensed tablets will be assessed as a measure of drug accountability.

These measures of compliance and drug accountability will be analyzed descriptively with mean, standard deviation, minimum and maximum by treatment group.

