
NAME OF COMPANY: HEXAL AG	NAME OF INVESTIGATIONAL MEDICINAL PRODUCT (IMP): Acetylcysteine 600 mg effervescent tablet	NAME OF ACTIVE INGREDIENT: acetylcysteine
	
smoking: ≥ 20 cigarettes daily)
 
[24] Use of snuff tobacco
 
[25] Legal incapacity and/or other circumstances rendering the patient unable to understand the nature, scope and possible consequences of the trial
 
[26] Subjects who are known or suspected:
 
 - not to comply with the trial directives - not to be reliable or trustworthy - to be a dependent person, e.g. a relative, family member, or member/ employee of the investigator's or sponsor's staff - subject is in custody or submitted to an institution due to a judicial order. 	
CLINICAL TRIAL CENTERS	Approximately 40 centers located in Germany, Bulgaria, Russia and Moldova.	
TEST PRODUCT	
Name: Acetylcysteine 600 mg effervescent tablet
 
Marketing authorization holder in Germany: HEXAL AG
 
Marketing authorization No: [REDACTED]
 
Formulation: effervescent tablet
 
Active substance: acetylcysteine
 
Strength: 600 mg acetylcysteine per effervescent tablet
 
Dosing schedule: over 14 days according to the randomized double-blind treatment (see randomization section)
 
Route of administration: oral; tablets should be taken during the meal (breakfast or lunch) dissolved in a glass of water (about 200 mL).
 
Manufacturer: [REDACTED]
	
PLACEBO TO TEST PRODUCT	
Name: Placebo
 
Formulation: effervescent tablet
 
Active substance/ Strength: none
 
Dosing schedule: over 14 days according to the randomized double-blind treatment (see randomization section)
 
Route of administration: oral, tablets should be taken during the meal (breakfast or lunch) dissolved in a glass of water (about 200 mL).
 
Manufacturer: [REDACTED]
	

[figure not shown]
NAME OF COMPANY: HEXAL AG	NAME OF INVESTIGATIONAL MEDICINAL PRODUCT (IMP): Acetylcysteine 600 mg effervescent tablet	NAME OF ACTIVE INGREDIENT: acetylcysteine
BLINDING	
The present trial will be double-blind.
 
The tablets containing the Test product and Placebo will be identical in their appearance and the labels will not contain any information about the identity of the respective product.
 
To maintain blinding, all patients will receive 4 tablets per day (2 tablets in the morning and 2 tablets at noon) provided in a daily kit.
	

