8.5.2 IMP Administration and Duration of Treatment

Patients will undergo a screening visit (Visit 1) within one day prior to randomization (Visit 2 or baseline visit).

Patients who meet the inclusion/ no exclusion criteria will be randomized to one of the following double-blind treatment on Day 1 (Visit 2):

- Group A: 600 mg acetylcysteine: one tablet test product plus three tablets placebo per day (to be taken as two tablets dissolved in a glass of water, twice daily) *OR*
- Group B: 1200 mg acetylcysteine: two tablets test product plus two tablets placebo per day (to be taken as two tablets dissolved in a glass of water, twice daily) *OR*
- Group C: 2400 mg acetylcysteine: four tablets test product per day (to be taken as two tablets dissolved in a glass of water, twice daily) *OR*
- Group D: Placebo: four tablets placebo per day (to be taken as two tablets dissolved in a glass of water, twice daily).

The IMP treatment period will last for 14 days but in case of delayed final visit (Visit 6) the patient can voluntarily take reserve study medication for a maximum of 3 additional days. The double-blinded medication will be dispensed to the patients on Day 1 (Visit 2).

The route of administration of the trial medication is described in sections 8.5.1.1 and 8.5.1.2.

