8.5.3 Packaging and Labelling

[REDACTED] (subcontracted by HEXAL AG) will pack and supply the trial medication together with sealed envelopes for unblinding in case of emergency.

Packaging, labelling and blinding will be according to GMP requirements, international and national laws and regulations.

The master labels will be prepared in English and translated into the respective local language(s).

[REDACTED] will ship the trial medication (in boxes of 4 patient kits inclusive emergency envelopes) to the respective central depot in the countries involved (*see below*).

Germany	
[REDACTED]
 
Contact person: [REDACTED] Phone: [REDACTED] mobile: [REDACTED] Email: [REDACTED]

Bulgaria	
[REDACTED]
 
Contact person: [REDACTED] mobile: [REDACTED] email: [REDACTED]

Russia	
[REDACTED]
 
Phone: [REDACTED]
 
Contact persons
 
[REDACTED]
 
Phone: [REDACTED] (ext. [REDACTED]) Fax: [REDACTED] mobile: [REDACTED] E-mail: [REDACTED]
 
[REDACTED]
 
Phone: [REDACTED] (ext. [REDACTED]) Fax: [REDACTED] mobile: [REDACTED] Email: [REDACTED]

Moldova	
[REDACTED]
 
Contact person: [REDACTED] mobile: [REDACTED] Email: [REDACTED]

The **randomized Patient Kit (box) carrying a tear-off label will include 14 Daily Kits** (numbered 1-14) and **one separate color-coded box with 3 Replacement/ Reserve Daily Kits** (numbered 1-3). The composition of one Patient Kit (box) is presented in [TF 1](#).

Each **Daily Kit** and the **Replacement/Reserve Daily Kits** will contain 2 tablets for the morning intake and 2 tablets for the noon intake. The composition of one Daily Kit is presented in [TF 2](#).

The **Replacement medication (in case of lost or damaged IMP) or the Reserve medication (in case of delayed final visit will be provided for 3 days and the voluntary use of this reserve medication will be documented in the patient diary.**

The Patient Kit (box) will be handed out to the patient on Visit 2 by the investigator.

[figure not shown]
PATIENT KIT for Randomization No.:

The Patient Kit is to be dispensed at Visit 2 and the tear-off label is to be affixed to the CRF

[figure not shown]

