7.2.7 Protocol Deviations

All protocol deviations will be listed by patient and will be discussed with the sponsor during the Blind Data Review Meeting before unblinding and database lock. Depending on the severity of protocol deviations (minor/major) the patients will be assigned to the respective statistical population.

Possible protocol deviations are discussed in a separate Protocol Deviation Management Plan.

The following categories of protocol deviations were defined in the Protocol Deviation Management Plan:

- Eligibility deviation,
- Withdrawal deviation
- Dosing deviation,
- Prohibited medication and therapies deviation
- Operational deviation

The final decisions regarding the severity of protocol deviations will be documented in a separate Protocol Deviation Report.

The occurred protocol deviations will be assessed by means of frequency tables, see Section [7.3.4.2](#).

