7.3.4.4 Treatment duration and time intervals between visits

The total duration of treatment will be calculated as the number of days between first and last intake of the IMP; these dates are documented in the CRF as start of treatment (date and time) and end of treatment (date and time).

$$\text{duration} = \text{date of end of treatment} - \text{date of start of treatment} + 1$$

This duration will be analyzed descriptively (mean, standard deviation, minimum and maximum) by treatment group for the safety set, the FAS and the PPS.

The time intervals between Visit 1 and Visit 2, Visit 2 and Visit 3, Visit 2 and Visit 4, Visit 2 and Visit 5 and between Visit 2 and Visit 6 will be assessed descriptively (mean, standard deviation, minimum and maximum) by treatment group for the safety set, the FAS and the PPS.

The start of treatment (month and year) is analyzed by means of frequency tables by treatment group for the safety set.

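### Reserve tablets taken after Day 14 count in the compliance numerator but not in the fixed denominator of 56, so compliance can reach 121.4% and can mask missed scheduled doses

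*SAP*

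**What the plan says.** SAP 7.3.4.3 sets the expectation: "In total it is expected that each patient takes 56 of the dispensed tablets", that is, 14 days with 2 tablets in the morning and 2 at noon. The measure follows from it: "Compliance (in %) will therefore be calculated as the number of tablets which were taken, as documented in the diary, divided by 56". The text puts no date limit on the numerator and no cap on the result. The section adds a drug accountability ratio, returned unused tablets over dispensed tablets. Both measures are summarised by treatment group with mean, standard deviation, minimum and maximum.

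Protocol 8.5.2 gives the planned length, "The IMP treatment period will last for 14 days", and then the exception for a late final visit: "the patient can voluntarily take reserve study medication for a maximum of 3 additional days". Protocol 8.5.3 supplies "one separate color-coded box with 3 Replacement/ Reserve Daily Kits" with every patient kit. Each of these holds 4 tablets, like an ordinary daily kit. The same section says that voluntary use of the reserve medication is recorded in the patient diary. It also gives the three kits a second purpose, to replace lost or damaged tablets.

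**The concern.** The numerator and the denominator cover different periods. The denominator is the scheduled 14-day course. The numerator is whatever the diary shows as taken, and the diary also holds reserve intake after Day 14. Elsewhere the SAP allows for the extension: section 7.3.4.4 measures treatment duration to the last intake, and section 7.4.2.2 describes the symptom score up to 3 days beyond Day 15. The compliance formula does not.

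Two things follow. A patient can exceed 100% while following the protocol exactly. More importantly, reserve tablets can offset scheduled tablets that were missed, so a figure of 100% no longer shows that the 14-day course was taken. Within a group mean, values inflated in this way also cancel genuine shortfalls in other patients. What is at stake is whether the reported compliance table describes intake during the planned treatment period.

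**Working it through.** **Inputs**

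- Tablets per day: 4 (Protocol synopsis, blinding; SAP 7.3.4.3).
- Scheduled days: 14 (Protocol 8.5.2).
- Reserve kits: 3, each of 4 tablets (Protocol 8.5.3).
- Numerator: all tablets recorded as taken in the diary (SAP 7.3.4.3), which includes reserve use (Protocol 8.5.3).

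**The plan's own figure.** 14 × 4 = 56, which matches the SAP. Reserve supply is 3 × 4 = 12, so each patient kit holds 56 + 12 = 68 tablets.

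**No missed dose, d reserve days.** Compliance under the SAP rule = (56 + 4d)/56.

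- d = 1: 60/56 = 107.1%
- d = 2: 64/56 = 114.3%
- d = 3: 68/56 = 121.4%, the ceiling

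**m scheduled tablets missed, all 12 reserve tablets taken after Day 14.** The SAP rule gives (56 − m + 12)/56. Compliance with the scheduled course is (56 − m)/56.

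| Scheduled tablets missed | SAP rule | Scheduled course |
|---|---|---|
| 4 | 64/56 = 114.3% | 52/56 = 92.9% |
| 8 | 60/56 = 107.1% | 48/56 = 85.7% |
| 12 | 56/56 = 100.0% | 44/56 = 78.6% |

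The gap is 12/56 = 21.4 percentage points in every row.

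**Does the accountability ratio reveal it?** Assume that all 68 tablets count as dispensed and that every tablet not taken is returned.

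- Perfect 14-day taker, reserve untouched: returns 12 reserve tablets, 12/68 = 17.6%.
- Patient who missed 12 scheduled tablets and took 12 reserve tablets: returns 12 scheduled tablets, 12/68 = 17.6%.

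Both patients also show 56/56 = 100% compliance, so the two statistics in SAP 7.3.4.3 are identical for them.

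**Effect on a group mean.** If a fraction f of a group takes all 12 reserve tablets after Day 14, the mean rises by f × 21.4 points. The documents give no value for f. The range runs from 0 if nobody does so to 21.4 if everybody does.

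**After correction (Day 1 to 14 tablets over 56).** The full taker who also used all reserve kits scores 56/56 = 100% instead of 121.4%. The patient who missed 12 scheduled tablets scores 44/56 = 78.6% instead of 100%.

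**Check of the obvious alternative denominator.** SAP 7.3.4.4 says: "The total duration of treatment will be calculated as the number of days between first and last intake of the IMP". Take a patient who stays in the trial but skips all of Days 12 to 14. Last intake is on Day 11, with 11 × 4 = 44 tablets taken. Dividing by 4 × duration gives 44/44 = 100%; dividing by the fixed 56 gives 44/56 = 78.6%. A duration-based denominator would therefore hide doses missed at the end of treatment.

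**The case against.** The best defence is that this is a descriptive safeguard with other checks around it. Daily kits are numbered 1 to 14 and reserve kits separately 1 to 3. Returned kits and diaries are checked at Visits 3 to 6, and the reserve kits specifically at Visit 6. The SAP lists medication returns by patient. The compliance maximum is tabulated, so values above 100% would be seen, and treatment duration would show dosing beyond Day 14. All of this stands, and it means that missed doses can be recovered from patient-level records. It does not repair the summary percentage. A masked patient sits at 100%, not above it, and a duration beyond Day 14 does not show that earlier doses were missed.

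Reserve kits used within Days 1 to 14 to replace lost or damaged tablets properly count towards the 56. That is also correct, and the fix must keep them.

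A reader might infer three stronger points that the documents do not support:

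- **That early stoppers are scored wrongly.** A patient who stops after Day 7 with full intake shows 28/56 = 50%. That is a legitimate measure of the planned course, and the SAP reports drop-out and treatment duration separately.
- **That per-protocol membership is affected.** SAP 7.2.7 lists "Dosing deviation" as a category, but no section sets a compliance threshold or ties this percentage to the Per Protocol Set. The separate deviation management plan is not among the documents.
- **That the patient shown at 100% should read 56/68 = 82.4%.** That figure is compliance over 17 days, a different quantity. Against the scheduled course the value is 78.6%.

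**Conclusion.** The point holds and is minor. As written, the compliance rule can return up to 121.4%, and can return 100% for a patient who took 78.6% of the scheduled tablets. This rests on reading the numerator literally, as every tablet the diary records as taken; nothing in the SAP excludes or caps reserve tablets. It needs a delayed Visit 6 and voluntary reserve use, and masking also needs missed scheduled doses. The 21.4-point distortion is therefore a per-patient ceiling, and its frequency is unknown. The figure is descriptive and does not enter the confirmatory analysis of the primary endpoint.

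**What to change.** In SAP 7.3.4.3, restrict the numerator to tablets taken on Days 1 to 14, including any replacement kit used in that window for lost or damaged tablets, and keep the denominator at 56. Report reserve intake after Day 14 separately, for example as the number of patients and of tablets by treatment group. Do not substitute treatment duration to last intake as the denominator.

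The cost is one clause in the SAP, a date condition in the derivation and one extra summary line. The SAP says that intake is recorded daily, morning and noon. The one thing to confirm is that the diary, which is not among the documents, dates reserve use so that intake up to Day 14 can be told apart from later intake. The change concerns the statistic only and leaves the dosing provisions as they are.

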7.3.4.4 Treatment duration and time intervals between visits

The total duration of treatment will be calculated as the number of days between first and last intake of the IMP; these dates are documented in the CRF as start of treatment (date and time) and end of treatment (date and time).

$$\text{duration} = \text{date of end of treatment} - \text{date of start of treatment} + 1$$

This duration will be analyzed descriptively (mean, standard deviation, minimum and maximum) by treatment group for the safety set, the FAS and the PPS.

The time intervals between Visit 1 and Visit 2, Visit 2 and Visit 3, Visit 2 and Visit 4, Visit 2 and Visit 5 and between Visit 2 and Visit 6 will be assessed descriptively (mean, standard deviation, minimum and maximum) by treatment group for the safety set, the FAS and the PPS.

The start of treatment (month and year) is analyzed by means of frequency tables by treatment group for the safety set.

7.4 Statistical Analysis of the Endpoints

7.4.1 Statistical Analysis of the Primary Endpoint

Efficacy of the test product will be shown by testing superiority of the three different doses in a hierarchical test procedure from the highest to the lowest dose compared to placebo.

Hierarchical ordered hypotheses will be tested at the type I error rate of $\alpha = 0.05$ (two-sided) until the first non-rejection. No error rate adjustment is required.

The set of hypotheses is as follows:

$$H_{01}: \mu_A = \mu_D \text{ versus } H_{11}: \mu_A \neq \mu_D,$$

$$H_{02}: \mu_B = \mu_D \text{ versus } H_{12}: \mu_B \neq \mu_D,$$

$$H_{03}: \mu_C = \mu_D \text{ versus } H_{13}: \mu_C \neq \mu_D.$$

Where μ_{group} denotes "mean change from baseline in the daily MSS over the entire treatment period" in treatment group (Group A, B, C or D) for the respective strength.

Superiority of the Test treatment over placebo (PL) is confirmed if the p-value is below 5% and a positive treatment effect is shown.

For the primary endpoint, analysis of covariance (ANCOVA) will be carried out using treatment and center as factors and baseline MSS as a covariate.

The SAS procedure PROC GLM will be used for that purpose.

Basically, the following code will be used:

```
proc glm data=primary;  
class treatment center;  
model mss=treatment center baseline_mss;  
estimate 'Group X vs D' treatment 1 -1 ;  
where treatment='X' or treatment='D';  
run;
```

The analysis will be performed for each hypothesis separately, i.e. only data of one active treatment group and the placebo group are included for the respective comparison.

The confirmatory analysis of the primary endpoint will be performed in the FAS.

In addition, the analyses used for the primary efficacy endpoint will be performed in the PPS. This analysis is intended to provide supportive evidence and will be considered descriptive.

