DATASETS FOR STATISTICAL ANALYSIS	
 • Safety Set: all randomized patients who received at least one dose of the trial medication. • Full-Analysis Set (FAS): all randomized patients who received at least one dose of the trial medication and who have at least one post-baseline assessment of MSS during the double-blind treatment period. • Per-Protocol Set (PPS): all FAS-evaluable patients who completed the double-blind treatment period without major protocol violations that could affect the efficacy evaluation. 	
STATISTICAL ANALYSIS	
Efficacy: Efficacy of the test product will be shown by testing superiority of the three different doses in a hierarchical test procedure starting from the highest to the lowest dose compared to placebo.
 
Hierarchical ordered hypotheses will be tested at the type I error rate of $\alpha=0.05$ (two-sided) until the first non-rejection. No error rate adjustment is required.
 
For the primary efficacy an endpoint analysis of covariance (ANCOVA) will be carried out using treatment and center as factors and baseline MSS as a covariate.
 
The trial will be powered to demonstrate superiority of the test product over placebo in the primary efficacy endpoint.
 
The confirmatory analysis of the primary endpoint will be performed in the FAS.
 
In addition, the analyses used for the primary efficacy endpoint will be performed in the PPS.
 
This analysis is intended to provide supportive evidence and will be considered descriptive.
	

NAME OF COMPANY: HEXAL AG	NAME OF INVESTIGATIONAL MEDICINAL PRODUCT (IMP): Acetylcysteine 600 mg effervescent tablet	NAME OF ACTIVE INGREDIENT: acetylcysteine														

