10.1 Statistical Analysis Plan

The statistical analysis plan (SAP) will be finalized prior to database lock. All relevant points related to the statistical analysis will be defined in the SAP. The main points are described in the following sections. In addition to these points the SAP will contain information on further topics (e.g., evaluation of baseline comparability of groups, different types of sensitivity analysis, handling of missing data, wrong treatment assignment, etc.).

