10.4 Statistical Tests

██████████ will write the **Statistical Analysis Plan (SAP)** for the present trial.

Efficacy:

Efficacy of the test product will be shown by testing superiority of the three different doses in a hierarchical test procedure from the highest to the lowest dose compared to placebo.

Hierarchical ordered hypotheses will be tested at the type I error rate of $\alpha=0.05$ (two-sided) until the first non-rejection. No error rate adjustment is required.

The set of hypotheses is as follows:

$$H_{01}: \mu_{2400} = \mu_{PL}$$

$$H_{11}: \mu_{2400} \neq \mu_{PL}$$

$$H_{02}: \mu_{1200} = \mu_{PL}$$

$$H_{12}: \mu_{1200} \neq \mu_{PL}$$

$$H_{03}: \mu_{600} = \mu_{PL}$$

$$H_{13}: \mu_{600} \neq \mu_{PL}$$

Where μ notes “mean change from baseline in the daily MSS over the entire treatment period” for the respective strength.

Superiority of the Test treatment over placebo (PL) is confirmed if the p-value is < 0.05 and a positive treatment effect is shown.

For the primary efficacy an endpoint, analysis of covariance (ANCOVA) will be carried out using treatment and center as factors and baseline MSS as a covariate.

The trial will be powered to demonstrate superiority of the test product over placebo in the primary efficacy endpoint.

The confirmatory analysis of the primary endpoint will be performed in the FAS.

In addition, the analyses used for the primary efficacy endpoint will be performed in the PPS.

This analysis is intended to provide supportive evidence and will be considered descriptive.

Safety:

The Safety Set will be used for the analysis of the safety data. All safety data obtained in this trial will be tabulated descriptively with descriptive group statistics (mean, standard deviation, minimum, maximum, number of valid cases) where appropriate.

AEs will be summarized by primary system organ class (SOC) and preferred term (PT). Severity and drug-event relationship of treatment emergent AEs are summarized separately. All adverse events will be listed.

Vitals signs, including changes from baseline will be summarized. A frequency table will be presented for abnormal values of laboratory parameters.

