5.5 Randomization

Each of the patients will be randomly assigned to one of the following groups.

- Group A: 600 mg acetylcysteine: one tablet test product plus three tablets placebo per day (to be taken as two tablets dissolved in a glass of water, twice daily) *OR*
- Group B: 1200 mg acetylcysteine: two tablets test product plus two tablets placebo per day (to be taken as two tablets dissolved in a glass of water, twice daily) *OR*
- Group C: 2400 mg acetylcysteine: four tablets test product per day (to be taken as two tablets dissolved in a glass of water, twice daily) *OR*
- Group D: Placebo: four tablets placebo per day (to be taken as two tablets dissolved in a glass of water, twice daily).

6 Definition of Endpoints

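### SAP 7.4.1 numbers its fixed-sequence hypotheses from the lowest dose up, against its own text and Protocol 10.4, which start at the highest dose

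*SAP*

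**What the plan says.** SAP 7.4.1 opens by stating that superiority is tested "in a hierarchical test procedure from the highest to the lowest dose compared to placebo". It continues: "Hierarchical ordered hypotheses will be tested at the type I error rate of" 0.05, two-sided, with testing to stop at the first hypothesis not rejected and no multiplicity adjustment. The numbered set that follows is H01: A against D, H02: B against D, H03: C against D.

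The letters are defined in SAP 5.5: "Group A: 600 mg acetylcysteine: one tablet test product plus three tablets placebo per day" and "Group C: 2400 mg acetylcysteine: four tablets test product per day". Group B is 1200 mg and Group D is placebo. Protocol 8.5.2 and 8.5.4 use the same letters for the same doses.

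Protocol 10.4 gives the same direction in words but labels its hypotheses by dose: H01 is 2400 mg, H02 is 1200 mg and H03 is 600 mg, each against placebo. The Protocol synopsis agrees: "in a hierarchical test procedure starting from the highest to the lowest dose compared to placebo".

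**The concern.** In a fixed-sequence procedure the order of the hypotheses is the multiplicity control. Each test can use the full 0.05 only because one order is settled before the data are seen and testing stops at the first failure. SAP 7.4.1 gives two opposite orders within a few lines, for the only confirmatory analysis in the trial.

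Two things are at stake:

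- **Loss of the 2400 mg claim.** If someone applied the numbered list, a non-significant 600 mg or 1200 mg result would block a claim for 2400 mg, however strong the 2400 mg result was.
- **A challenge to pre-specification.** If the discrepancy were noticed and settled only after unblinding, and the two orders led to different conclusions, a reader could fairly ask when the order was chosen.

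**Working it through.** **1. The passages side by side**

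| Source | First | Second | Third |
|---|---|---|---|
| Protocol synopsis, in words | highest | – | lowest |
| Protocol 10.4, in words | highest | – | lowest |
| Protocol 10.4, numbered | 2400 mg | 1200 mg | 600 mg |
| SAP 7.4.1, in words | highest | – | lowest |
| SAP 7.4.1, numbered (letters from SAP 5.5) | A = 600 mg | B = 1200 mg | C = 2400 mg |

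Four of the five statements agree. Only the SAP's numbered list is reversed. No sentence in either document states or justifies a lowest-first order.

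**2. Reproducing the plan's sample size**

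Inputs from Protocol 10.5 and SAP 5.4: mean change 5.4 on test and 4.5 on placebo (difference 0.9), SD 3.4, two-sided alpha 0.05, power 80%, allocation 1:1:1:1.

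- n per group = 2 × [(1.960 + 0.8416) × 3.4 / 0.9]² = 224.03, rounded up to 225; 4 × 225 = 900. The plan's figures reproduce.
- Standard error of a difference = 3.4 × √(2/225) = 0.3206.
- Expected z-statistic = 0.9 / 0.3206 = 2.808.
- Power of one comparison = Φ(2.808 − 1.960) = Φ(0.848) = 0.802. With the noncentral t on 448 degrees of freedom it is 0.800.

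**3. Power to claim 2400 mg under each order**

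Assume the planned difference of 0.9 at every dose. The three z-statistics share the placebo arm and the groups are equal in size, so each pair has correlation 0.5.

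- Stated order (2400 mg first): the claim needs only the C against D test, so the power is 0.802.
- Numbered order (600 mg first): the claim needs all three tests to succeed. Conditioning on the placebo mean, expressed as a standard normal c, the probability is ∫ φ(c) [Φ(1.199 + c)]³ dc, where 1.199 = √2 × 0.848. The result is 0.614.

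A simulation of 200,000 trials using separate pairwise t-tests, each with its own two-arm variance as SAP 7.4.1 specifies, gives 0.801 and 0.612. Centre and baseline adjustment were not modelled.

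With equal effects, the chance of at least one claim is about 80% in either order. What changes is which dose can be claimed.

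**4. Sensitivity to smaller effects at lower doses**

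The documents give no dose-specific effects, so these differences are assumptions, shown for range only.

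| Assumed difference at 2400 / 1200 / 600 mg | 2400 mg claim, stated order | 2400 mg claim, numbered order |
|---|---|---|
| 0.9 / 0.9 / 0.9 | 80% | 61% |
| 0.9 / 0.6 / 0.3 | 80% | 12% |
| 0.9 / 0.45 / 0.225 | 80% | 7% |

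**5. Type I error**

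Under the global null, either order fixed in advance gives a simulated familywise error of 0.050. If the starting end were left open until the data were seen, the chance of rejecting at least one of the two candidate first tests would be about 9% two-sided.

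**The case against.** The strongest reply is that this is a typographical matter and the intended order is not in doubt. Every sentence in both documents says highest to lowest. The SAP sentence heads the same section as the list. The list can be read as giving the set of hypotheses rather than their sequence, and its alphabetical order matches the table list in SAP 8.1. SAP 7.4.1 also runs each comparison separately, with generic code and no sequential gate. All three p-values will therefore be produced anyway, and the order enters only when they are interpreted, beside a sentence that says highest first. Protocol 10.4 fixes the order in words and numbers, so resolving to 2400 mg first would follow the documented plan.

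Most of this stands. It makes actual misapplication unlikely, and the 61% is a worst case rather than a forecast. It does not remove the contradiction. Protocol 10.4 introduces its list in the same way and does number it in testing order, so a reader would expect the SAP's numbers to mean the same.

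Precedence is also not settled. Of its own statistical sections, Protocol 10.1 says: "The main points are described in the following sections". SAP section 4 describes the SAP as covering what the protocol does not. Both favour the protocol's order. But Protocol 10.1 also leaves the definition of all relevant statistical points to the SAP, which points the other way, and neither document contains a formal precedence clause.

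**Conclusion.** The concern holds. SAP 7.4.1 contradicts itself and Protocol 10.4 on the order of the confirmatory tests. The most likely cause is that the hypotheses were listed alphabetically by group letter.

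If the stated order is followed, the cost is zero. If the numbered order were applied, power for the 2400 mg claim would drop from 80% to about 61%. That figure rests on a difference of 0.9 at every dose, SD 3.4, 225 per arm and no covariate adjustment. The drop would be larger if the lower doses work less well, which the documents do not quantify. There is no alpha inflation as long as one order is fixed beforehand.

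The correction is essential because of where the error sits and because a clean remedy is available only until unblinding, not because misapplication is likely.

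**What to change.** Before database lock and unblinding, relabel the hypotheses in SAP 7.4.1 to match Protocol 10.4:

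- H01: μ_C = μ_D (2400 mg against placebo)
- H02: μ_B = μ_D (1200 mg against placebo)
- H03: μ_A = μ_D (600 mg against placebo)

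Add one sentence stating that this numbering is the order of testing. The change concerns only the statistical testing order and uses the order the sponsor already states in the synopsis, in Protocol 10.4 and in the SAP's own text.

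The cost is three relabelled lines and one sentence in the SAP. The protocol, the sample size, alpha and the data collection do not change.
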